6.6.1 COVID-19 Vaccination Guidance

Authorized/approved COVID-19 vaccines can be given to patients in this study. Investigators should follow the Clinical Study Protocol and their local prescribing information and policies when considering if vaccination against COVID-19 is appropriate for their patients.

If you are considering vaccinating your patient against COVID-19, please consider the following:

- For a specific vaccine, consider the potential impact of its relevant labeling information (i.e., “Indications,” “Contraindications,” “Warnings and Precautions,” “Adverse Reactions”) on its use in the study population and individual subject.
- Please contact the manufacturer of the COVID-19 vaccine if you have any questions concerning their product.

To better assess the overall impact of COVID-19 vaccination on a particular study and study population, ensure that both the COVID-19 vaccination details (including brand name and manufacturer) is captured in eCRF as concomitant medication, and adverse reactions are reported.

6.6.2 Additional concomitant treatment

- Pre-medication will not be required, but may be utilized following the first doses of the investigational products. This includes management of nausea, diarrhea, and vomiting. If a patient has a known history of nausea and vomiting with prior therapy, it is strongly recommended that prophylactic anti-emetics be initiated at the start of treatment (see Section 8.4.5.2).
- Blood and blood product transfusions, including platelet infusions, are allowed at any time during the study, except to meet inclusion criteria.
- Patients already taking erythropoietin at the time of screening for the study may continue it provided they have been taking it for more than one month at the time study treatment is started.
- Granulocyte colony stimulating factors (GCSFs) are permitted for use at the discretion of the Investigator.
- Patients should avoid corticosteroids during the study. If treatment with corticosteroids is indicated, the Investigator should discuss with the Medical Monitor. If in the interest of patient safety the Investigator must treat the patient immediately and a discussion is not feasible, the Medical Monitor should be notified in writing.
- Patients may receive treatment with bisphosphonates or denosumab for the treatment of bone metastases.
- Patients should avoid medications or drugs that increase risk for seizure (e.g., tricyclic antidepressants, pseudoephedrine, anesthetics, amphetamines, cocaine).
- Patients may receive treatment with megestrol acetate when prescribed for appetite stimulation.
- Patients may take low molecular weight heparin. It is recommended that patients treated with an anticoagulant should have their anticoagulation monitored carefully and dose adjusted accordingly.

6.6.3 Other concomitant treatment

Other medication than that described above, which is considered necessary for the patient's safety and wellbeing, may be given at the discretion of the Investigator and recorded in the appropriate sections of the eCRF.

6.7 Dose modification

Please refer to each modular-specific appendix for details on dose reduction.

Management of AZD4635-related toxicities and related dose modifications can be found in Section 8.4.5.

6.8 Treatment after the end of the study

After this study primary DCO, the clinical study database will be closed to the entry of new data. Patients receiving their assigned study treatment at the time of the primary DCO will be

able to continue to receive study treatment if, in the opinion of the Investigator, they are still deriving clinical benefit.

Patients who remain on study treatment after the primary DCO will be managed by the Investigator according to routine clinical practice if not specified differently in the study modules. It is generally recommended to continue observing ongoing patients at the frequency indicated within the study plans as described in the SoA, however the assessments are at the Investigators' discretion based on the individual case. Restrictions regarding concomitant medications (Section 6.6) will be followed while the patient is receiving the IP(s). Study treatment will be supplied to sites outside of the IWRS. Drug dispensation and reconciliation will be performed by the site on each patient visit. Serious adverse events, overdose and pregnancy will be reported after the last dose of study treatment, for the duration stated in the relevant module, using a paper form.

Study will be open until last patient treated. Final Last Subject Last Visit will be defined as last patient's treatment discontinuation.

If study drug is approved on market for use in disease under study indication, patients may be discontinued and switched to marketed product. Drug supply options can be available depending on the country and will be proposed to patient when found as best way to continue treatment by both AZ and investigator.

7 DISCONTINUATION OF TREATMENT AND PATIENT WITHDRAWAL

7.1 Discontinuation of study treatment

Patients that discontinue 1 study drug may remain on the study and receive other study drug(s) as long as they are continuing to derive clinical benefit (see Section 8.4.6). Patients may be discontinued from study drug(s) in the following situations:

- Patient decision. The patient is at any time free to discontinue treatment, without prejudice to further treatment.
- Any AE that, in the opinion of the Investigator or AstraZeneca, contraindicates further dosing or meets the criteria for discontinuation as defined in the dose modification guidance or prescribing information for the study drug(s).
- Investigator decision or severe non-compliance with the Clinical Study Protocol
- Confirmed disease progression unless, in the opinion of the Investigator, the patient is still receiving clinical benefit. Patients will continue study treatment until objective disease progression, or beyond RECIST 1.1 defined progression if patient is receiving clinical benefit, as judged by the Investigator and in the absence of discontinuation criteria. Tumor assessment must continue while patient continues to receive study treatment as per Section 8.1.1.

- Patients incorrectly initiated on study drug(s) (e.g., patient is determined to have met one or more of the exclusion criteria for study participation at study entry and continuing investigational therapy might constitute a safety risk)
- Patient started alternative anticancer therapy including another investigational agent
- Patient lost to follow-up

Note that discontinuation from study treatment is NOT the same thing as a complete withdrawal from the study.

See the SoA of the assigned module for data to be collected at the time of treatment discontinuation and follow-up and for any further evaluations that need to be completed. The reason for study drug and combinational agent discontinuation will be recorded in the eCRF.

7.1.1 Procedures for discontinuation of study treatment

The Investigator should instruct the patient to contact the site before or at the time if study treatment is stopped. Discontinuation of study treatment, for any reason, does not impact the patient's participation in the study. A patient that decides to discontinue study treatment will always be asked about the reason(s) and the presence of any AEs. The date of last intake of study treatment and the combinational agent should be documented in the eCRF. All study treatment should be returned by the patient at his next on-site study visit or unscheduled visit. Patients permanently discontinuing study treatment should be given locally available standard of care therapy, at the discretion of the Investigator.

The patient should continue attending subsequent study visits and data collection should continue according to the study protocol. If the patient does not agree to continue in-person study visits, a modified follow-up must be arranged to ensure the collection of endpoints and safety information. This could be a telephone contact with the patient, a contact with a relative or treating physician, and/or information from medical records. The approach taken should be recorded in the medical records. A patient who agrees to modified follow-up is not considered to have withdrawn consent or to have withdrawn from the study.

7.1.2 Procedures for patients who test positive for COVID-19

During the study, COVID-19 tests may be prescribed, if required, and in accordance with local guidance. If a patient tests positive, their continued participation in the study and their treatment with the study drugs will be discussed with the Medical Monitor.

7.2 Lost to follow-up

A patient will be considered potentially lost to follow-up if he fails to return for scheduled visits and does not reply to contact attempts by site personnel.

The following actions must be taken if a patient fails to return to the clinic for a required study visit:

- Site personnel must attempt to contact the patient and reschedule the missed visit as soon as possible and counsel the patient on the importance of maintaining the assigned visit schedule.
- Before a patient is deemed lost to follow-up, the Investigator or designee must make every effort to regain contact with the patient or next of kin (e.g. repeat telephone calls, certified letter to the patient's last known mailing address or local equivalent methods). These contact attempts should be documented in the patient's medical record.
- Efforts to reach the patient should continue until the end of the study. Should the patient be unreachable at the end of the study, the patient should be considered to be lost to follow-up with unknown vital status at end of study and censored at latest follow-up contact.

7.3 Withdrawal from the study

A patient may withdraw from the study (e.g., withdraw consent) at any time (study drug(s) and assessments) at his own request, without prejudice to further treatment. The reason for patient withdrawal will be recorded in the eCRF.

If a patient decides to withdraw from the study, including study treatment, the investigator needs to confirm whether the patient:

- Withdraws consent to all further participation in the study including any further follow up (e.g., survival contact telephone calls)

OR

- Withdraws consent from study treatment, but agrees to follow-up procedures (as defined in Section 7.1).

A patient who considers withdrawing from the study must be informed by the Investigator about modified follow-up options (e.g., telephone contact, contact with a relative or treating physician, or information from medical records).

If the patient withdraws consent for disclosure of future information, the Sponsor may retain and continue to use any data collected before such a withdrawal of consent.

If a patient withdraws consent to the use of mandatory biological samples, the samples will be disposed of/destroyed if possible and the action documented. If samples have already been analyzed, the sponsor is not required to destroy the results of this research.

A patient who withdraws consent will always be asked about the reason(s) and the presence of any AEs. The Investigator will follow up with patients as medically indicated.

In the event that the patient has actively withdrawn consent to the processing of his personal data, the vital status of the patient can be obtained by site personnel from publicly available resources where it is possible to do so under applicable local laws

See the SoA in the relevant module for data to be collected at the time of study drug discontinuation and follow-up and for any further evaluations that need to be completed. All study drug should be returned by the patient.

8 STUDY ASSESSMENTS AND PROCEDURES

Study procedures and their timing are summarized in the core SoA. For all assessments after screening, see the module-specific SoA.

The Investigator will ensure that data are recorded on the eCRF as specified in this clinical study protocol and in accordance with the instructions provided. The Medidata Rave electronic data capture (EDC) system will be used for data collection and query handling.

The Investigator will ensure the accuracy, completeness, and timeliness of the data recorded and the provision of answers to data queries according to the Clinical Study Agreement. The Investigator will sign the completed eCRFs. A copy of the completed eCRFs will be archived at the study site.

Immediate safety concerns should be discussed with the Sponsor immediately upon occurrence or awareness to determine if the patient should continue or discontinue study treatment.

Adherence to the study design requirements, including those specified in the SoA, is essential and required for study conduct.

All screening evaluations must be completed and reviewed to confirm that potential patients meet all eligibility criteria. The Investigator will maintain a screening log to record details of all patients screened and to confirm eligibility or record reasons for screening failure, as applicable.

Procedures conducted as part of the patient's routine clinical management (e.g., blood count) and obtained before signing of the ICF may be utilized for screening or baseline purposes, provided the procedures met the protocol-specified criteria and were performed within the time frame defined in the SoA.

The number of samples taken, as well as the volume required for each analysis, may be changed during the study as emerging data become available. However, the estimated total volume of blood that will be drawn from each patient in this study during screening and the

first cycle of treatment will not exceed 300 mL (over a 1-month period). Any additional requirements are specified within the module.

8.1 Efficacy assessments

All patients are expected to have both CT/MRI/PET and bone scans at each scheduled disease assessment. Evaluation of objective tumor response in this study will be done using RECIST v1.1 Criteria in evaluable soft tissue disease (see [Appendix G](#)). Tumors will be assessed at screening according to the module-specific SoA. Reassessment of tumors will be done by the same methods used to establish baseline tumor measurements.

PCWG3 PSA criteria ([Appendix I](#)) will also be used to evaluate response and progression. These criteria will be followed for determining the change in PSA levels. Prostate-specific antigen (PSA) levels in this study will be measured at screening, at the start of each new treatment cycle, at the end of study visit, at any other timepoints indicated in the SoA, and as clinically indicated.

Disease progression will be deemed to have occurred if 1 or more of the following criteria is met:

- Soft tissue disease progression as defined by RECIST v1.1
- Bone lesion progression by PCWG-3 ([Table 7](#))
- Death

Patients with PSA progression are permitted and encouraged to continue treatment until symptomatic or radiographic progression. Sites should monitor PSA by cycle but plan to continue through early rises for a minimum of 12 weeks unless there is other evidence of progression.

All CT/bone scans and all imaging assessments performed for RECIST 1.1 tumour assessment will be reviewed at site. Duplicates must be available at the site in readiness to be sent for retrospective independent central RECIST 1.1 review, if deemed appropriate. More information on this procedure is available in the Image Acquisition Guideline for this study.

8.1.1 Tumor assessments with RECIST v1.1

RECIST version 1.1 guidelines for measurable and non-measurable target lesions (TLs) and non-target lesions (NLTs) and the objective tumor response criteria are presented in [Appendix G](#).

Baseline tumor assessments should encompass all areas of known predilection for metastases in the disease under evaluation and should additionally investigate areas that may be involved based on signs and symptoms of individual patients. Baseline assessments should be

performed no more than 28 days before the start of study treatment, and ideally should be performed as close as possible to the start of study treatment. The methods of assessment used at baseline should be used at each subsequent follow-up assessment.

The first follow-up assessment should be initially at 6 weeks (± 1 week) following the start of AZD4635 dosing and subsequent assessments will be performed every 2 cycles (every 8 weeks ± 1 week) thereafter. Any other sites at which new disease is suspected should also be appropriately imaged. If an unscheduled assessment is performed and the patient has not progressed, every attempt should be made to perform subsequent assessments at the scheduled visits.

Categorization of objective tumor response assessment will be based on the RECIST Version 1.1 guidelines for response of soft tissue lesions: CR (complete response), PR (partial response), SD (stable disease), and PD (progression of disease). For patients who only have non-measurable TLs at baseline, categorization of objective tumor response assessment will be based on the RECIST Version 1.1 guidelines for response for NTLs: CR, PD, and Non CR/Non PD.

If the Investigator is in doubt as to whether progression has occurred, particularly with response to NTLs or the appearance of a new lesion, it is advisable to continue treatment and reassess the patient's status at the next scheduled assessment or sooner if clinically indicated.

To achieve "unequivocal progression" on the basis of non-target disease, there must be an overall level of substantial worsening in non-target disease such that, even in presence of SD or PR in target disease, the overall tumor burden has increased sufficiently to merit discontinuation of therapy. A modest "increase" in the size of one or more NTLs is usually not sufficient to qualify for unequivocal PD status.

Calculation or derivation of tumor response variables

At each visit, patients will be programmatically assigned a RECIST visit response of CR, PR, SD or PD depending on the status of their disease compared to baseline and previous assessments.

Progression of TLs will be calculated in comparison to when the tumor burden was at a minimum (i.e., smallest sum of diameters previously recorded on study, nadir). In the absence of progression, tumor response (CR, PR, SD) will be calculated in comparison to the baseline tumor measurements obtained before starting treatment.

If a patient has had a tumor assessment that cannot be evaluated, then the patient will be assigned a visit response of NE, unless there is evidence of progression in which case the response will be assigned as PD.

For TL measurements, if $\leq 1/3$ of the TL sizes are missing then a scaling-up rule will be applied as follows:

1. If $\leq 1/3$ of lesions recorded at baseline are missing then the results will be scaled up (based on the nadir sizes) to give an estimated sum of diameters and this will be used in calculations (this is equivalent to comparing the visit sum of diameters of the non-missing lesions to the nadir sum of diameters excluding the lesions that are missing and determining at what rate the lesions are changing).
2. If $> 1/3$ of lesions recorded at baseline are missing then the TL response will be NE. However, if the sum of non-missing TL diameters would result in PD (i.e., if using a value of 0 for missing lesions the sum of diameters has still increased by $> 20\%$ or more compared to the smallest sum of diameters on study), PD takes precedence over NE.
3. A visit response of CR will not be allowed if any of the TL data are missing.

Objective response rate is defined as the proportion of patients with measurable disease at baseline who have a confirmed ORR per RECIST v1.1. For the analysis of objective response rate an “evaluable-for-response” population will be derived and will exclude patients who do not have measurable disease at baseline.

A visit response of CR is defined when all TL and NTL lesions present at baseline have disappeared (with the exception of lymph nodes which must be $< 10\text{mm}$ to be considered non-pathological) and no new lesions have developed since baseline. A visit response of PR is defined when the sum of diameters of the TLs has decreased by 30% or more compared to baseline (with no evidence of progression) and the NTLs are at least stable with no evidence of new lesions.

In the case of SD (patients who have neither progressed nor achieved at least a PR and are evaluable), measurements should have met the SD criteria at least once after the study start.

When the Investigator is in doubt as to whether PD has occurred and therefore reassesses the patient at a later date, the date of the initial scan should be declared as the date of progression if the repeat scans confirm progression.

Percentage change from baseline in tumor size will be determined for patients with measurable disease at baseline and is derived at each visit by the percentage change in the sum of the diameters of TLs.

For further details see [Appendix G](#) of this CSP.

CCI

CCI [Redacted]

It is important to follow the assessment schedule as closely as possible. Please refer to the Study Plan in each module and [Appendix G](#).

8.1.2 PCWG3 bone lesions assessment

Categorization of tumor progression of bone lesions will be based on the PCWG-3 criteria. Bone lesions will be assessed by bone scintigraphy commonly performed with Technetium-99 (bone scans) or PET scan. Positive hot spots on the bone scan should be considered significant and unequivocal sites of malignant disease to be recorded as metastatic bone lesions (see [Appendix G](#)).

The requirements for determination and confirmation of radiographic progression by either bone scan (bone progression) or CT/MRI (soft tissue progression) are summarized in [Table 7](#).

Table 7 Requirements for documentation of progression

Visit Date	Criteria for Bone Progression	Criteria for Soft Tissue Progression
First visit after baseline (expected at week 6 after the start of AZD4635 study treatment)	
 2 or more new lesions compared to baseline bone scan. Requires confirmation at least 6 weeks later with ≥ 2 additional lesions compared to the first scan after baseline 	
 Progressive disease on CT or MRI by RECIST v1.1 Requires confirmation at least 4 weeks (but no more than 8 weeks).
From the 2 nd visit onwards post-baseline	
 2 or more new lesions compared to the first bone scan after baseline. Requires confirmation at least 6 weeks later for persistence or increase in number of lesions 	
 Progressive disease on CT or MRI by RECIST v1.1 No confirmation required.

CT, Computed tomography; MRI, Magnetic resonance imaging; RECIST, Response Evaluation Criteria in Solid tumours.

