8.2.8.2 Progression-free follow-up visits

Patients who discontinue study treatment prior to the occurrence of objective PD will be followed with PSA samples and CT/MRI/PET and bone scans every 3 months (± 1 week) from the last date of the last tumor response assessment until either: objective PD has been confirmed, withdrawal of consent, until the primary analysis DCO, or until the study or module is terminated by the Sponsor.

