FDG-PET has gained acceptance as a valuable tool for detecting, staging and restaging several malignancies. If FDG-PET scans are included in a protocol, an FDG uptake period of 60 minutes prior to imaging has been decided as the most appropriate for imaging of patients with malignancy. Whole-body acquisition is important since this allows for sampling of all areas of interest and assessment if new lesions have appeared thus determining the possibility of interval progression of disease. Images from the base of the skull to the level of the mid-thigh should be obtained 60 minutes post injection. PET camera specifications are variable and manufacturer specific, so every attempt should be made to use the same scanner, or the same model scanner, for serial scans on the same patient. Whole-body acquisitions can be performed in either 2- or 3-dimensional mode with attenuation correction, but the method chosen should be consistent across all patients and serial scans in the clinical study.

PET/CT scans

At present, low dose or attenuation correction CT portions of a combined PET/CT are of limited use in anatomically based efficacy assessments and it is therefore suggested that they should not be substituted for dedicated diagnostic contrast enhanced CT scans for tumor measurements by RECIST Version 1.1. In exceptional situations, if a site can document that the CT performed as part of a PET/CT is of identical diagnostic quality to a diagnostic CT (with IV and oral contrast) then the CT portion of the PET/CT can be used for RECIST measurements. However, this is not recommended because the PET portion of the CT introduces additional data that may bias an Investigator if it is not routinely or serially performed.

ASSESSMENT OF BONE LESION PROGRESSION USING PCWG3 CRITERIA

Bone lesions will be assessed by bone scan in addition to being part of the RECIST v1.1 malignant soft tissue assessment.

Method of assessment

Bone lesions identified on a whole body isotopic bone scan at baseline should be recorded and followed by the same method as per baseline assessment.

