In the D8731C00001 study isotopic bone scans will be used as a method of assessment to identify the presence of new bone lesions at follow-up visits. New lesions will be recorded where a positive and unequivocal hot-spot that was not present on the baseline bone scan assessment is identified on a bone scan performed at any time during the study. The Investigator should consider the positive hot-spot to be a significant new site of malignant disease and represent true disease progression in order to record the new lesion.

Tumor progression evaluation

Schedule of the evaluation

Baseline assessments should be performed no more than 28 days before the start of study treatment. The first follow-up assessment for Modules 1, 2, and 3 should be initially at 6 weeks (± 1 week) following the start of AZD4635 dosing and subsequent assessments will be performed every 2 cycles (8 weeks, ± 1 week) thereafter.

If an unscheduled assessment was performed and the subject has not progressed, every attempt should be made to perform the subsequent assessments at their originally scheduled visits. This schedule is to be followed in order to minimize any unintentional bias caused by some subjects being assessed at a different frequency than other subjects.

Documentation of lesions

All bone lesions (or sites of disease) should be identified by a bone scan at baseline. Their status should be followed at subsequent visits. At each visit an overall assessment of the bone lesion progression should be recorded by the Investigator. This section provides the definitions of the criteria used to determine and record bone progression at the investigational site at each visit.

Progression on a bone scan is identified using PCWG3 as follows:

- At the first bone scan post-baseline (6 weeks):
2 or more new metastatic bone lesions are observed on the first 6-week scan compared to the baseline assessment. The confirmatory scan, performed at least 6 weeks later and preferably no later than the next scheduled visit for a bone scan (i.e., Week 12), must show 2 or more additional new metastatic bone lesions (for a total of 4 or more new metastatic bone lesions since the baseline assessment) for progression to be documented.

Note - The first bone scan completed after baseline will be considered the ‘6-week scan’ regardless if taken at week 6 or at an unscheduled assessment.

- After the first bone scan post-baseline (6 weeks):

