2 or more new metastatic bone lesions are observed compared to the 6-week assessment. The confirmatory scan, performed at least 6 weeks later and preferably at the next scheduled visit for a bone scan, must show the persistence of or an increase in the number of metastatic bone lesions compared to the prior scan for progression to be documented.

The date of progression is the date of the scan that first documents the second lesion.

Evaluation of bone progression status

Table 15 provides the definitions for the visit bone progression status for bone lesions.

Table 15 Bone progression status

Non Progressive Disease (Non-PD)	No evidence of progression, or appearance of one new bone lesion, or non-fulfillment of the progression criteria including new lesions without confirmation of progression.
Progressive Disease (PD)	Bone lesions fulfilling the requirements for at least 2 new lesions and confirmation of progression.
Not Evaluable (NE)	Only relevant if a follow-up bone scan is not performed

OVERALL RADIOLOGICAL VISIT ASSESSMENT

Table 16 provides the definitions how the visit responses for soft tissue (according to RECIST1.1 criteria) and bone progression status (according to PCWG3 criteria) are combined to give an overall radiological objective visit response.

Table 16 Overall radiological visit response

Overall visit soft tissue response (RECIST 1.1)	Bone progression status (PCWG3)	Bone lesions at visit Present/Absent	Overall radiological visit response
CR	Non-PD	Absent	CR
CR	Non-PD	Present	PR
CR	NE	-	PR
PR	Non-PD or NE	Any	PR
SD	Non-PD or NE	Any	SD
NED	Non-PD or NE	Any	Non-PD
NE	Non-PD or NE	Any	NE

Table 16 Overall radiological visit response

Overall visit soft tissue response (RECIST 1.1)	Bone progression status (PCWG3)	Bone lesions at visit Present/Absent	Overall radiological visit response
PD	Any	Any	PD
Any	PD	Any	PD

CR = complete response, PR = partial response, SD = stable disease, PD = progressive disease, NE = not evaluable, NED = No Evidence of Disease (only relevant when there is no TL and NTL from baseline).

CONFIRMATION OF RESPONSE

In the D8731C00001 study, imaging for confirmation of response (CR or PR) should be performed at the next scheduled RECIST and PCWG3 assessment, i.e., 8 weeks (and must not be less than 4 weeks later) following the date the criteria for response were first met.

Table 17 Best overall response when confirmation of CR and PR required.

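### Section 8.1.2 lets PET replace the bone scan, but Appendix G and the rPFS rule recognise only the bone scan, so such visits can count as missed

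*Protocol*

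**What the plan says.** **Core text.** Section 8.1.2 gives two ways to assess bone: "Bone lesions will be assessed by bone scintigraphy commonly performed with Technetium-99 (bone scans) or PET scan". Section 8.1 reads: "All patients are expected to have both CT/MRI/PET and bone scans at each scheduled disease assessment". Section 8.2.8.2 says that patients who stop treatment before progression "will be followed with PSA samples and CT/MRI/PET and bone scans every 3 months". Table 2 (Section 1.3) and Section 4.1.2 use the same CT/MRI/PET label at screening.

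**Appendix G, bone.** At baseline: "Bone lesions identified on a whole body isotopic bone scan at baseline should be recorded and followed by the same method as per baseline assessment". Afterwards: "isotopic bone scans will be used as a method of assessment to identify the presence of new bone lesions at follow-up visits". Table 15 allows the NE status for bone, with the condition: "Only relevant if a follow-up bone scan is not performed".

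**Appendix G, soft tissue.** Table 11 lists CT and MRI for target lesions and places FDG-PET under new lesions only. On the low-dose or attenuation-correction CT part of a PET/CT, "it is therefore suggested that they should not be substituted for dedicated diagnostic contrast enhanced CT scans for tumor measurements". An exception is allowed where the site documents diagnostic quality.

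**rPFS (Section 9.4.4).** A visit with the soft-tissue scan (MRI/CT) but no bone scan, or the reverse, is a missed assessment. Progression or death after two or more missed visits is censored at the last evaluable assessment before them.

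**The concern.** A site that relies on the section defining bone assessment may use PET and stay within the protocol. The parts of the protocol that turn images into endpoints do not recognise that choice. Two things follow for rPFS, a secondary endpoint whose named summary is the 6-month proportion.

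- The same visit is evaluable under one rule and missed under another, so an event can be kept or censored depending on which passage is programmed.
- Bone progression visible only on PET has no defined status.

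Because reassessment is to use the baseline method, a PET choice made at baseline tends to carry through follow-up.

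**Working it through.** No figure in the protocol is in dispute here. The check traces the modality rules through the tables.

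**1. Schedule (Section 8.1.1).** The first follow-up scan is at week 6, then every 8 weeks: 6, 6 + 8 = 14, 14 + 8 = 22. Week 22 lies before the 6-month estimate (about 26 weeks).

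**2. PET replaces the bone scan; CT/MRI is done.** Take stable soft tissue at weeks 6 and 14 and soft-tissue progression at week 22. That is the third follow-up scan, so Table 7 asks for no confirmation.

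| Rule | Week 6 | Week 14 | Week 22 | rPFS result |
|---|---|---|---|---|
| Table 15, bone status | NE | NE | NE | – |
| Table 16, overall visit | SD + NE = SD | SD + NE = SD | PD + any = PD | event at week 22 |
| Section 9.4.4, missed-visit rule | missed | missed | PD after 2 missed visits | censored before week 6 |

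Week 6 is the first scheduled follow-up, so the last evaluable assessment before the two missed visits is the baseline one. Losing an event in this way moves the 6-month estimate upward. A single such visit does not trigger censoring; two or more are needed.

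**3. Bone progression seen only on PET.** The rule of two or more new lesions with confirmation (Table 7, Appendix G) is written for bone scans. Without a bone scan, Table 15 gives NE, not PD. For a patient with no soft-tissue lesions, Table 16 maps no evidence of disease plus bone NE to Non-PD. Such patients are expected, because Section 6.5.1 stratifies on bone-only metastasis. The FDG-PET algorithm in Appendix G belongs to the soft-tissue part and gives no PCWG3 bone status.

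**4. ORR when PET replaces the bone scan.** Under Table 16, CR + NE = PR, PR + NE = PR and SD + NE = SD. A responder is CR or PR, so responder status is unchanged. Only the CR/PR split can move.

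**5. ORR when PET replaces CT/MRI at a follow-up visit.** Target lesions are then unmeasured and the visit is NE, unless progression is shown or the CT part of a PET/CT qualifies. Under Table 17, PR followed by NE gives SD or NE, so the response is not confirmed.

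For scale only, the planning case of 5/20 = 25% has a Clopper-Pearson interval with lower limit Beta(0.025; 5, 16) and upper limit Beta(0.975; 6, 15). That is 8.7% to 49.1%, as the synopsis states. One responder lost gives 4/20 = 20.0% (5.7% to 43.7%). This shows what one case would do; it is not an estimate of what will happen.

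**The case against.** The strongest reply is that Section 8.1 already expects a bone scan at every scheduled assessment and that Table 2 and 8.2.8.2 list it separately from CT/MRI/PET. Within 8.1.2 itself, the hot-spot rule and Table 7 speak of the bone scan for bone and CT/MRI for soft tissue. A site following 8.1 has its bone scan and the problem does not arise. This stands to the extent that substitution for the bone scan rests on 8.1.2 alone. It does not remove the conflict, because 8.1.2 is the section that defines how bone is assessed.

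A reader might infer that PET-assessed visits become non-evaluable for ORR as well as rPFS, or that ORR falls by 1/20 = 5 percentage points for each measurable patient followed by PET. The documents do not support either as a general result. Table 16 preserves responder status when only the bone scan is replaced. Measurable disease is defined on CT or MRI at baseline, so a patient imaged only by PET at baseline does not enter the ORR population. A patient measured by CT/MRI at baseline is to be followed by the same method, so a switch to PET departs from the plan. The PET/CT exception, the precedence of progression over NE, and replacement of non-evaluable patients at the sponsor's discretion limit the effect further.

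The module schedules and the Image Acquisition Guideline are not in the text reviewed and may narrow what sites actually do.

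**Conclusion.** The point holds in a limited form. The protocol permits PET for bone in one section and gives no way to score it in the sections that derive rPFS. The missed-visit rule and Table 16 then disagree on the same visit. The consequence is possible censoring of rPFS events after two or more such visits, and no defined status for bone progression seen only on PET.

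ORR is touched only indirectly, if the CT/MRI/PET label leads a site to replace CT/MRI with PET at a follow-up visit without a diagnostic-quality CT component.

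No overall magnitude can be given, because the share of PET-only visits is not stated. The week-22 example assumes a literal reading of Section 9.4.4 and PET in place of the bone scan at both earlier visits.

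**What to change.** - **Section 8.1.2:** delete PET as an alternative to the bone scan, so that the section agrees with Appendix G.
- **Table 2 and Sections 4.1.2, 8.1 and 8.2.8.2:** state that PET is additional. It may identify new soft-tissue lesions as described in Appendix G, with that appendix's PET/CT exception, and it does not replace CT/MRI or the isotopic bone scan.

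Writing a PET scoring rule for bone into Appendix G and Section 9.4.4 would also reconcile the text, but it needs a new lesion-counting definition. Deletion is simpler.

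The cost is protocol wording and a reminder to sites. No procedure is added, since bone scans are already expected at each assessment and CT or MRI is already required for target lesions. Table 16 and the missed-visit rule would still differ when a bone scan is missed for another reason. One sentence saying which governs rPFS would settle that, if the SAP does not already do so.
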